7.2.8 Rey–Osterrieth complex figure test [52] (Appendix 9)

The Rey–Osterrieth complex figure test (ROCF) is a neuropsychological assessment in which examinees are asked to reproduce a complicated line drawing, first by copying it freehand (recognition), and then drawing from memory (recall). Many different cognitive abilities are needed for a correct performance, and the test therefore permits the evaluation of different functions, such as visuospatial abilities, memory, attention, planning, and working memory (executive functions). First proposed by Swiss psychologist André Rey in 1941[53] and further standardized by Paul-Alexandre Osterrieth in 1944 [54], it is frequently used to further explain any secondary effect of brain injury in neurological patients, to test for the presence of dementia.

7.2.9 Digit Span Test- Forward and Backward [55, 56] (Appendix 10)

A digit-span task is used to measure working memory's number storage capacity. The tester reads a series of numbers of different lengths and asks the subject to immediately repeat in the forward or reverse direction. The digit span gradually increases from 3 to 10 in the forward test, and gradually increases from 2 to 8 in the reverse test. Each digit span includes two tests. The test was terminated when both of the two tests were performed incorrectly by the subject. The longest digit length that a subject can speak is its digit span.

7.2.10 Verbal Fluency Tests [57] (Appendix 11)

The test is mainly sensitive to frontal dysfunction and mild semantic memory impairment. Subjects are asked to speak as many words as possible within a given time (usually 1 minute), such as the name of an animal, fruit or vegetable. Record the correct number of words, repetitions, series and conversions. The correct number of words is usually used as a scoring indicator, but other factors such as concatenation and conversion can sometimes be used as scoring indicators. The number of series is the items listed consecutively in each sub-category, counting from the second item of each sub-category until the subject is converted to another sub-category, and the series of each sub-category are added to obtain the total series. The total number of series, mainly reflecting the semantic memory function. The number of conversions is the times the subject switches between subcategories, mainly reflecting the frontal lobe execution function.

7.2.11 Trail Making Test: Parts A and B [58] (Appendix 12)

Part A consists of 25 circles, numbered 1 through 25, and the tester instructs the participant to draw lines as fast as possible in increasing numerical order. Part B is also composed of 25 circles, but these circles are white circles (1-12) and black circles (1-13). Subjects need to alternately connect circles of different colors in numerical order. The completion performance of the subject is determined based on the number of correctly completed lines and the time required to complete. Although both the A test and the B test rely on visual motion and perceptual scanning skills, trail making test B requires

considerable cognitive flexibility to complete the black and white transition connection under time pressure.

7.2.12 Boston Naming Test (BNT) [59] (Appendix 13)

The BNT requires the participant to name objects depicted in outline drawings. In our modification of the full BNT, only 30 items are presented. The drawings are graded in difficulty, with the easiest drawings presented first. If a participant encounters difficulty in naming an object, a stimulus cue and/or a phonemic cue is provided. Record the correct number of independent initial naming, clue naming, and option naming.

7.2.13 Activities of daily living (ADL) [60] (Appendix 14)

The ADL scale can evaluate the daily activities of the subject comprehensively, accurately and quickly. It consists of the physical life self-care scale and the instrumental ADL. There are 14 items, including two parts: first, the physical life self-care scale has a total of 6 items, including toilet, eating, dressing, grooming, walking and bathing; second, instrumental ADL has a total of 8 items, including call, shop, prepare meals, do housework, laundry, use transportation, take medicine and financing abilities. The higher the subject scores, the worse the ability of daily living.

7.2.14 Clinical Dementia Rating (CDR) [61] (Appendix 15)

The CDR is a refinement of information that the doctor obtains through conversations with the patient and his/her family, and to assess the degree of impairment of the patient's cognitive function, and then to quickly assess the severity of the patient's condition. The assessment of cognitive domains consists of six items: memory, orientation, judgment and problem solving, work and social ability, family life and hobbies, and independent living ability. The judgment is in five levels, "normal CDR=0, suspected dementia CDR=0.5, mild dementia CDR=1, moderate dementia CDR=2, severe dementia CDR = 3". The CDR-SOB (CDR sum of box) total score is a simple sum of the scores of the six items. CDR sum of boxes adds up the 6 items, and the total score ranges from 0 to 18. As long as the score is greater than 0, the subject has at least one cognitive impairment. Generally, the change value of CDR sum of boxes can be used in clinical trials to obtain more accurate cognitive evaluation[62]. CDR is a widely used measure of the severity of dementia.

7.3 Procedures for genetic studies

7.3.1 Gene testing

The goal of the genetic study of CFAN is the genetic information and useful biological materials (DNA, blood, cerebrospinal fluid, urine, saliva, etc.) provided by cognitive normal and dementia in the ADAD cohort and unknown gene mutation cohort. It is anticipated that collection of these data will facilitate clinical and basic science investigations of the pathogenesis of dementia.

7.3.2 Detection of pathogenic genes and risk genes

After informed consent of the study subjects, we extract 3 ml of the peripheral venous blood of the participants. Peripheral blood genomic DNA is extracted using whole blood genomic DNA extraction kit. *ApoE*, *PSEN1*, *PSEN2* and *APP* gene primer design are referenced. *ApoE*, *PSEN1*, *PSEN2*, and *APP* gene are screened by polymerase chain reaction (PCR). The PCR products above are subjected to Sanger sequencing. The sequencing results are analyzed by DNASTAR (version 7.1) software. The single nucleotide polymorphism gene mutation screening was performed with reference to the PubMed/GeneBank database.

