Recently, in our study, 3330 patients with AD or mild cognitive impairment in 514 pedigrees were enrolled from the CFAN. 13.12% of pedigrees carried *PSENs/APP* missense mutations, 3.71% carried *PSENs/APP* synonymous/untranslated region variants, and 83.17% did not carry *PSENs/APP* mutations. In the present study, 11 missense mutations were first identified by the CFAN, including 10 in *PSEN1* and one in *APP*. The present study highlights that the FAD population in China needs extensive investigation, and a concerted effort is necessary to identify the crucial pathological genes underlying the pathogenesis of AD.

2. Introduction

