2.4 Sample size

There will be a total of 40,000 subjects participating in this project. The total number of subjects to be included in this hospital is 5,000, and other sites include 400-600 persons per sites.

3. Research aims

This research will establish and continuously improve the FAD research network in conjunction with multi-center institutions nationwide. By collecting information on the family's demography, genetics, neuropsychology, neuroimaging, biomarkers and other information, we can understand the current FAD population in China, clarify the genetic characteristics, pathogenesis, disease characteristics and diagnosis and treatment status of AD in China; which will lay the foundation for ameliorating clinical diagnosis and treatment, establishing a Chinese FAD clinical database and an international cooperative research platform.

3.1 To set up a multi-center, nationwide FAD research network and database platform in China

The network and database include ADAD cohort of the known mutations of *PSEN1*, *PSEN2* and *APP* (mutation carriers and noncarriers; pre-symptomatic and symptomatic) and unknown mutations cohort.

3.2 To clarify the epidemiological characteristics of FAD in China.

Conduct a comprehensive FAD epidemiological survey in China to clarify the impact of different nationalities, regions, gender, age, living environment (rural/urban), education level, etc. on the

occurrence and development of the disease.

3.3 To clarify the genetic characteristics of FAD in China.

This project is to discover new FAD mutation sites, pathogenic genes, to protective genes, to explore the pathogenic and protective mechanism, to analyze the disease development laws of families with different sizes of FAD in China, and to clarify the frequency distribution of mutant genes in the Chinese FAD population.

3.4 To clarify the clinical characteristics and disease development laws of FAD in China.

The project will collect and regularly follow-up the samples (blood, urine and saliva etc.) and data (neuropsychology, imaging etc.) in the cohort. Emphasis is placed on the occurrence and development of asymptomatic mutant gene carriers from asymptomatic to symptomatic periods.

3.5 To discover and verify the early diagnosis biomarkers of AD.

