6.1 Participant population

All participants enrolled in CFAN were adults, and at least two first-degree relatives had AD. All participants received clinical assessment and genetic testing at baseline. Based on whether carrying a pathogenic mutation of the *PSEN1*, *PSEN2*, or *APP*, the cohort was further divided into two subgroups: autosomal dominant AD and unknown gene mutation FAD (un-FAD).

Subjects come from three sources:

1) FAD family in the memory clinic of Xuanwu Hospital.

2) FAD family recruited from CFAN subsites, where recruitment was according to the study protocol.

3) Online registration through the CFAN website (www.Chinacfan.org) and submission of basic demographic data and family information to CFAN. The CFAN administrator selects the family that meets inclusion criteria by reviewing the online registration materials, and recommends them to the CFAN subsite or Xuanwu Hospital memory clinic according to the geographical location.

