7.3.3 Gene risk locus detection

We performed whole exon sequencing and whole genome sequencing on some families. Case-control methods were used to discover, study and analyze risk-related risk sites, providing genetic basis for disease prevention and control.

The peripheral blood DNA is extracted, and the genomic DNA is interrupted by ultrasound, and sequenced after the process of building a library, hybridization capture, and quality control. SNPs were annotated with CCDS, human genome database, and dbSNP information to determine the genes, coordinates, mRNA sites, amino acid changes, and SNP functions (missense mutations/nonsense mutations/variable cleavage sites) at which mutation sites occur, SIFT predicts that SNP affects protein function prediction and so on.

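### The only APP/PSEN1/PSEN2 test applied to everyone does not measure gene dosage and can miss a primer-site deletion, so un-FAD and the mutation frequency should be limited to what the methods detect

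*Protocol*

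**What the plan says.** - **Who is tested, and how.** Section 6.5 item 5 tests all participants at baseline for APOE and the three causal genes. Section 7.3.2 amplifies the genes by PCR and then states: "The PCR products above are subjected to Sanger sequencing". It describes the purpose as follows: "The single nucleotide polymorphism gene mutation screening was performed with reference to the PubMed/GeneBank database".
- **What the result decides.** Section 6.1 uses carriage of a pathogenic mutation in PSEN1, PSEN2 or APP as the dividing line: "the cohort was further divided into two subgroups: autosomal dominant AD and unknown gene mutation FAD (un-FAD").
- **The second method.** Section 7.3.3: "We performed whole exon sequencing and whole genome sequencing on some families". It is presented as case-control work on risk sites. On processing it says: "SNPs were annotated with CCDS, human genome database, and dbSNP information". It gives neither the number of families nor how they were chosen, and it does not say that a result changes a family's subgroup.
- **What is to be reported.** Aim 3.3 is "to clarify the frequency distribution of mutant genes in the Chinese FAD population". Section 1 already reports that "13.12% of pedigrees carried *PSENs/APP* missense mutations", that 3.71% carried synonymous or untranslated-region variants, and that the remaining 83.17% carried no mutation in these genes.

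**The concern.** A Sanger read of a PCR product shows which bases are present, not how many copies of the gene there are. A third copy with normal sequence reads as normal. If a heterozygous deletion removes a primer site, only the intact allele amplifies, and that also reads as normal. The protocol names no dosage or copy-number method, yet the result of this test is the basis for an unqualified split into ADAD and un-FAD.

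Three things are at stake:

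- **The split.** A family whose disease comes from such a change in a known gene is labelled as having an unknown gene mutation.
- **The gene search.** That family then sits among those searched for new genes, although the cause lies in a known one.
- **The frequency.** Aim 3.3 speaks of mutant genes without limiting the variant type, and Section 4.3 plans to compare gene frequencies with Western reports. Such a comparison is interpretable only if the detectable variant types are stated.

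**Working it through.** **1. The path of a family with a dosage change or primer-site deletion, following the protocol as written.**

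| Step | Place | Outcome |
|---|---|---|
| Baseline test | 6.5 item 5; 7.3.2 | PCR and Sanger read normal |
| Subgroup | 6.1 | No pathogenic mutation found, so un-FAD |
| Exome/genome sequencing | 7.3.3 | Only if the family is among those selected; SNP annotation described |
| Reclassification | none stated | Stays un-FAD |
| Frequency | Section 1; aim 3.3 | Counted as carrying no mutation |

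No step recovers the family by rule.

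**2. The reported percentages.** The three classes sum to 13.12 + 3.71 + 83.17 = 100.00, with no copy-number or deletion class. Section 1 gives them for 514 pedigrees, but they do not reproduce on that base:

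- 67/514 = 13.04% and 68/514 = 13.23%, not 13.12%
- 19/514 = 3.70%, not 3.71%
- 427/514 = 83.07% and 428/514 = 83.27%, not 83.17%

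On 404 they fit exactly: 53/404 = 13.12%, 15/404 = 3.71%, 336/404 = 83.17%, and 53 + 15 + 336 = 404. Of all denominators from 50 to 600, only 404 fits all three. It is also the number of pedigrees in the title of item 30 in the reference list. This is a separate matter to reconcile. The calculation below uses percentages only and does not depend on it.

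**3. Possible size.** Let s be the share of the 83.17% that carries an undetected structural change in one of the three genes. The protocol gives no value, so the range for s is assumed, and none is allowed for in the 3.71% class.

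- Missense or structural share = 13.12 + 83.17 × s
- Share truly without a mutation = 83.17 × (1 − s)
- Missed part of the combined share = 83.17 × s / (13.12 + 83.17 × s)

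| s (assumed) | Missense or structural | Truly none | Missed part |
|---|---|---|---|
| 0% | 13.12% | 83.17% | 0% |
| 0.5% | 13.54% | 82.75% | 3.1% |
| 1% | 13.95% | 82.34% | 6.0% |
| 2% | 14.78% | 81.51% | 11.3% |
| 5% | 17.28% | 79.01% | 24.1% |

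The second column is a different quantity from the 13.12%, which counts missense only. The table shows how far an all-type frequency could lie above a missense-only one. It is not an error in the 13.12%.

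**The case against.** Several fair points can be made for the protocol.

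- **Other sequencing is planned.** Section 4.3 promises current sequencing technology to find new mutation sites in APP, PSEN1 and PSEN2, and the annotation list in 7.3.3 is open-ended. Calling details may sit in a laboratory manual. This stands as far as it goes: copy-number calling is not excluded. But neither section names it, coverage is partial, and no place says a result moves a family. The classification rule belongs to the protocol, which states it in 6.1.
- **un-FAD is already a residual label.** It says the mutation is unknown, not absent. That softens the label, but not the statement in Section 1 that the remaining pedigrees carried none.
- **No such family is documented.** The protocol nowhere says that structural changes occur in this cohort, and the missing class in Section 1 is equally consistent with there being none. This stands: the bias is conditional and its size has no anchor.

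Two stronger readings are tempting and should not be drawn. A reader might infer that the 13.12% is biased low. It is labelled as missense, and missed duplications or deletions cannot change a missense frequency. A reader might also infer that missed carriers enter the Section 8 mixed model as noncarriers. Section 3.1 places carriers and noncarriers inside the known-mutation cohort and lists the unknown-mutation cohort apart. Section 8 does not say that un-FAD members supply the noncarriers, so that effect is not shown.

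**Conclusion.** The point holds in limited form. The one test applied to everyone cannot exclude a dosage change or a primer-site deletion in the three genes, and no stated step corrects the label afterwards. Any affected family would be misfiled as un-FAD and counted among the 83.17%, and an all-type mutation frequency could only be too low.

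The direction follows from the assay; the size cannot be set from the document. Under an assumed 0.5% to 5% of negative pedigrees, the missense-or-structural share would be 13.5% to 17.3%. The upper end, with about 24% of that share missed, comes entirely from the assumed 5% and is not an estimate. The consequences rest on the ADAD/un-FAD split, the search for new genes and the wording of the frequency.

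**What to change.** 1. In Section 7.3.3, add copy-number and indel calling for APP, PSEN1 and PSEN2 in the exome and genome data already generated. State that a family with a pathogenic result is moved to ADAD before the Section 8 analyses.
2. In Section 6.1 and aim 3.3, define un-FAD as no pathogenic APP/PSEN1/PSEN2 variant detected by the methods applied. Report the frequency as that of pathogenic sequence variants, a lower bound for all variant types, and state which families had Sanger sequencing only.

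The word pathogenic must stay in the definition. If un-FAD required that no sequence variant at all be found, the 3.71% of pedigrees with synonymous or untranslated-region variants would fit neither subgroup unless their variant is pathogenic.

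The cost is some bioinformatic work on existing data and a more narrowly stated frequency. Families tested by Sanger only remain unresolved, and the revised wording would say so.

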7.3.3 Gene risk locus detection

We performed whole exon sequencing and whole genome sequencing on some families. Case-control methods were used to discover, study and analyze risk-related risk sites, providing genetic basis for disease prevention and control.

The peripheral blood DNA is extracted, and the genomic DNA is interrupted by ultrasound, and sequenced after the process of building a library, hybridization capture, and quality control. SNPs were annotated with CCDS, human genome database, and dbSNP information to determine the genes, coordinates, mRNA sites, amino acid changes, and SNP functions (missense mutations/nonsense mutations/variable cleavage sites) at which mutation sites occur, SIFT predicts that SNP affects protein function prediction and so on.

7.3.4 Body fluid testing

Detection of cerebrospinal fluid, blood, urine and saliva biomarkers in each group, including routine testing items such as blood, urine routine, biochemistry, electrolytes, coagulation function, cerebrospinal fluid routine, biochemical and other indicators. Also including special indicators cerebrospinal fluid and blood A β ₄₀, A β ₄₂, t-tau, p-tau and neurogranin. We conduct body fluid testing to study and explore early diagnostic markers of disease, and predictors of risk progression.

7.3.5 Blood specimens

Blood was taken on an empty stomach in the morning. Each subject received 8 ml of peripheral blood, 5 ml was injected into the purple head anticoagulation tube, and 3 ml was injected into the red head non-anticoagulated tube. The blood collection tube was marked with the name and number, and centrifuged within 2 hours. The purple head anticoagulation tube was centrifuged at 2000 rpm for 10 minutes to aspirate the upper layer of plasma; the remaining specimens were retained in the anticoagulation tube. After the red head non-anticoagulation tube was centrifuged at 2000 rpm for 10 minutes, the serum was aspirated and placed in two 1.5 ml centrifuge tubes, about 500 μ l/tube, and the non-anticoagulant tube was discarded. The name and number of the specimen and the type of specimen (the serum is labeled Q and the plasma is J) are indicated on the centrifuge tube. The centrifuge tube was immediately stored at -80 ° C, and the anticoagulation tube was stored in a refrigerator at -20°C.

7.3.6 Cerebrospinal fluid specimens

Lumbar puncture needs to be performed in the morning. To eliminate the impact of puncture bleeding on the quality of cerebrospinal fluid specimens, the first 1-2 ml of CSF should be discarded. 10 ml of cerebrospinal fluid was collected, centrifuged within 2 hours after collection (2000 rpm / 10 minutes of centrifugation), and the supernatant was aspirated and placed in 10 1.5 ml centrifuge tubes, 1 ml/tube. Ten centrifuge tubes were immediately stored in a -80°C freezer.

Approximately 1 ml each of CSF and plasma samples will be utilized for assessment of the various defined measures. CSF will be analyzed for $A\beta_{1-40}$, $A\beta_{1-42}$, tau and ptau181 measured via ELISA-based methods. Plasma will be analyzed for $A\beta_{1-40}$, $A\beta_{x-40}$, $A\beta_{1-42}$, and $A\beta_{x-42}$. The remaining aliquots will be banked at - 80°C.

7.4 Imaging

A model of how different AD biomarkers change during the development of the AD proposed that biomarkers became abnormal in the following order:

- (1) β -amyloid (indicating deposition of amyloid in plaques outside the cell, measured in CSF and by amyloid PET)
- (2) Tau (indicating the formation of tau fibrils with the neurons)
- (3) Glucose metabolism (measured on PET, indicating damage to neurons)
- (4) Structural MRI (indicating damage to brain structure)
- (5) Cognitive impairment

At the time of each assessment, participants will undergo scanning with MRI and PET. The PET imaging will include both FDG and PIB scans to measure metabolism and $A\beta$ deposition, respectively.

Xuanwu Hospital and each sub-center have advanced imaging equipment, including cyclotron RDS111 (Siemens) and GE's PET/MR full body scanner. It has the license for the use of radioactive drugs by the National Food and Drug Administration (the fourth category) and has the qualification to prepare new drugs (tracer) for research and development.

7.4.1 Magnetic resonance imaging (MRI)

MRI is a medical imaging technique used in radiology to form pictures of the anatomy and the physiological processes of the body in both health and disease. MRI scanners use strong magnetic fields, magnetic field gradients, and radio waves to generate images of the organs in the body. MRI does not involve X-rays or the use of ionizing radiation. MRI is widely used in hospitals and clinics for medical diagnosis, staging of disease and follow-up without exposing the body to radiation. The contrast provided between grey and white matter makes MRI the best choice for many conditions of the central nervous system, including demyelinating diseases, dementia, cerebrovascular disease, infectious diseases, Alzheimer's disease and epilepsy.

All MRIs should be scheduled prior to the lumbar puncture procedure. All participants will be screened for standard MRI contraindications immediately before the MRI. Scanning will start with placement of stereotactic marker on participant's right temple and proper orientation of head in coil. All participants will then undergo the following imaging: T1 weighted image (T1WI), T2 weighted image (T2WI), blood oxygenation level dependent (BOLD), Diffusion tensor imaging (DTI), arterial spin labeling (ASL), magnetic resonance angiography (MRA).

